## 9.4 Statistical Methodology

### 9.4.1 Data Summary

All continuous data will be summarized using continuous descriptive statistics: number of subjects with responses (n), mean, standard deviation, median, minimum, and maximum. Changes from baseline, where appropriate, will be calculated as the follow-up measure minus the baseline measure, where baseline is defined as the last measure prior to the AccuLIF spinal system surgical procedure.

### 9.4.2 Sample Size Calculation

CONFIDENTIAL

This material is the property of Stryker Spine. Do not disclose or use except as authorized in writing by Stryker.  
Page 27

Sample size calculations are based on the primary analysis of the change from baseline in segmental lordosis at 12 months, utilizing a one-sided, one-sample t-test. Based on previous experience it is assumed that the true change in segmental lordosis after 12 months will be 5 degrees. It is also determined that a change of at least 3 degrees is considered clinically meaningful. With a standard deviation of up to 6 degrees and assuming 90% power, 79 subjects are required to show a difference of at least 3 degrees. Assuming a dropout rate of up 20%, 100 subjects will be enrolled.

#### **9.4.3 Interim Analysis and Early Stopping Considerations**

There are no planned interim analyses.

#### **9.5 Efficacy Patient Population**

All patients enrolled in the study with any follow-up efficacy assessment (radiographic assessment) will be included in the efficacy patient population.

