This material is the property of Stryker Spine. Do not disclose or use except as authorized in writing by Stryker.  
Page 11

Ancillary Devices	
The AccuLIF system is indicated for use with autogenous bone and/or allograft (cancellous or corticocancellous allograft chips) and supplemental fixation. Stryker supplementation fixation (Xia or ES2 pedicle screws must be used as part of the study protocol).

Statistical Methodology	
All continuous data will be summarized using continuous descriptive statistics: number of subjects with responses (n), mean, standard deviation, median, minimum, and maximum. Changes from baseline, where appropriate, will be calculated as the follow-up measure minus the baseline measure, where baseline is defined as the last measure prior to the AccuLIF spinal system surgical procedure.
 
All categorical data will be summarized using counts and percentages. Denominators for percentages will be the number of subjects in the respective patient population with nonmissing data.
 
For the primary endpoint of an increase of 3 degrees or more of segmental lordosis, a one-sided analysis (<math>\alpha=0.05</math>) will be used to assess significance. A one-sample t-test will be employed. Although the primary analysis will be at 24 months, similar analyses will be performed at each visit. Both the change from baseline and the results at each visit will be summarized.
 
For all other radiographic parameters, the change from baseline will be analyzed at each visit using two-sided, one-sample t-tests (<math>\alpha=0.05</math>) comparing the change from baseline to 0.
 
Secondary and exploratory endpoints will be analyzed where appropriate. Where changes from baseline can be calculated for numerical data, statistical analyses will be performed. Analyses will follow the two-sided approach taken for the primary analyses. Data that is ordinal in nature, such as the changes in clinical outcomes, may be analyzed using Wilcoxon signed rank tests, comparing baseline measures to follow-up measures. All analyses will be two-sided and evaluated at an alpha level of 0.05.

CONFIDENTIAL

This material is the property of Stryker Spine. Do not disclose or use except as authorized in writing by Stryker.  
Page 12

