## 9 Statistical Plan

### 9.1 Efficacy Parameters

#### 9.1.1 Primary Objective Parameters

The primary objective parameters of this study are the change in pre-operative to post-operative radiographic outcomes of a cohort treated for degenerative disease at one or two levels implanted with the AccuLIF spinal system at one level via TLIF procedure with supplemental fixation. The primary objective will be evaluated at 12 months post-operatively.

Primary Radiographic parameters are defined as:

- Disc height (anterior, middle, posterior in millimeters)
- Foraminal height (in millimeters)
- Segmental lordosis (at each TLIF level in degrees)
- Regional Lordosis: (inferior endplate T12-S1 in degrees)
- Sagittal balance: (C7-S1 in millimeters)

  

- Success is defined as an increase of 3 degrees or more of segmental lordosis 12 months post operatively.

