#### 9.1.4 Secondary Objective Parameters

The secondary parameters of the study, evaluated at each study visit, are as follows:

- Surgical parameters of the AccuLIF cohort, including operative time, estimated blood loss and length of stay.
- The occurrence of neurologic complications, defined as abnormal changes from the pre-operative to post-operative neurologic evaluations.
- Changes in clinical outcomes, comparing pre- and post-operative patient measured outcomes defined as VAS, ODI and quality of life (QOL) as measured by SF-12.
- The occurrence and frequency of additional complications of the AccuLIF cohort, including infection and nonunion.
- Standard radiographic outcomes defined as; fusion status, cage placement, migration / subsidence and parameters of supplemental fixation hardware including screw placement and subsidence.

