## 9.3 Missing Data

The primary analyses will be based on observed data. In addition, sensitivity analyses will be performed including missing data using a Markov Chain Monte Carlo multiple imputation method and using the last observation carried forward.

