#### **9.6 Safety Patient Population**

All patients who undergo the surgical procedure (lumbar interbody fusion via the transforaminal approach with the AccuLIF Expandable Interbody Fusion Cage with internal supplemental fixation in the form of pedicle screws) will be included in the safety patient population.

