## 10.3 Early Withdrawal of Subjects

### *When and How to Withdraw Subjects*

In the event that the subject is discontinued by the investigative center prior to the final study evaluation, the subject will be notified by the center that he/she is no longer in the study and a Study Termination CRF will be completed.

The following is a list of reasons for which subjects may be withdrawn and the date of termination that should be used on the Study Termination CRF in each situation. This list is not all inclusive:

Termination Reason	Date of Termination
Death	Date of death
Investigative center termination	Date of study close-out visit
Lost to follow-up	Date Stryker termination approval given
Voluntary withdrawal	Date subject notified center of withdrawal
Removal of study device	Date of removal procedure
Study device not implanted	Date of surgery
Surgery not performed	Date Stryker termination approval given

At the time of study surgery it is required that the following components are implanted: AccuLIF interbody implant, supplemental fixation via pedicle screws, bone graft (autogenous and / or corticocancellous allograft chips).

CONFIDENTIAL

This material is the property of Stryker Spine. Do not disclose or use except as authorized in writing by Stryker.  
Page 29

Revision or removal of the AccuLIF Cage System constitutes a failure and study termination for the subject.

If revision of supplemental fixation is required during the study, the event is considered a reoperation and does not constitute a failure or study termination.

If the subject fails to return for his/her follow-up appointments, every effort should be made to contact the subject to assess his/her health status. If, after attempting to contact the subject through three documented phone calls and a certified letter, the subject still does not respond, he/she will be considered lost to follow-up. A Study Termination CRF will be completed **only after notifying Stryker of the subject's status and being given approval to terminate.**

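### Section 9.5 admits only patients with a follow-up film to the sole efficacy population, which on the natural reading drops film-less treated subjects from the questionnaire analyses and the multiple imputation

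*Combined protocol and SAP*

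**What the plan says.** Section 9.5 sets the entry rule: "All patients enrolled in the study with any follow-up efficacy assessment (radiographic assessment) will be included in the efficacy patient population". The parenthesis limits the qualifying assessment to imaging.

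Section 9.6 defines the only other population, for safety: "All patients who undergo the surgical procedure". It sets no follow-up condition.

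Sections 9.1.1 to 9.1.7 all stand under the heading "9.1 Efficacy Parameters". Among them, section 9.1.4 lists as secondary parameters: "Changes in clinical outcomes, comparing pre- and post-operative patient measured outcomes defined as VAS, ODI and quality of life (QOL) as measured by SF-12".

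On missing data, section 9.3 says: "The primary analyses will be based on observed data". It adds that "sensitivity analyses will be performed including missing data using a Markov Chain Monte Carlo multiple imputation method and using the last observation carried forward". It names no population for either step.

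For percentages, the synopsis says: "Denominators for percentages will be the number of subjects in the respective patient population with nonmissing data".

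Section 10.3 adds: "Revision or removal of the AccuLIF Cage System constitutes a failure and study termination for the subject".

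**The concern.** Membership of the efficacy population depends on something that happens after surgery. That matters most in a single-arm study, where no comparator is selected in the same way.

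Two groups are exposed:

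- **Questionnaires but no film.** These subjects have observed VAS, ODI or SF-12 scores. Those scores do not depend on an image, yet want of an image would set them aside.
- **No film at all.** These subjects left before the first scheduled film, or never had one. The multiple imputation in section 9.3 is the one planned analysis that could represent them. If it is run in the section 9.5 population, a check on missing data is made in a set from which the subjects with the most missing data have already been removed.

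At stake are avoidable loss of collected patient-reported data and a weaker robustness check. Power and the primary test are not at stake.

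**Working it through.** **1. The plan's own figures.** Section 9.4.2 gives a true change of 5 degrees, a threshold of 3, an SD of 6 and 90% power for a one-sided one-sample t-test; section 9.1.3 sets alpha at 0.05. The difference to detect is 5 − 3 = 2.

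- Normal approximation: (6 × (z0.95 + z0.90) / 2)² = 77.07, so 78.
- Noncentral t: n = 79, power 0.902. This matches the plan.
- Dropout: 79 / 0.80 = 98.75, so 99; the plan enrols 100.
- Power with 98, 95, 90 or 80 subjects with film: 0.949, 0.943, 0.932 or 0.905.

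The sample size is sound, and the film rule is not a power problem.

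**2. Which population applies to which analysis.** The plan does not say. Three facts point the same way: the patient-reported outcomes are under the efficacy heading, the section 9.5 set is the only efficacy set, and no text assigns these outcomes elsewhere. This is an inference, though nothing contradicts it.

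**3. Where the rule changes a result.**

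| Analysis | Effect of the film condition |
|---|---|
| Lordosis t-test on observed data | None: without a film there is no value to test |
| Radiographic percentages | None: denominators already count only nonmissing data |
| Last observation carried forward, lordosis | None: there is no post-operative film value to carry |
| VAS, ODI, SF-12 on observed data | Scores of subjects with no film are left out |
| Multiple imputation (9.3) | Treated subjects with no film are left out |

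**4. Whether such subjects can arise.** The documents foresee them.

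- Section 11.6 lists images not done, and images that cannot be evaluated, as deviations separate from a missed visit.
- Section 15.3 allows for an insurer refusing to pay for radiographs, with reimbursement decided case by case.
- Under section 10.3, cage revision or removal ends participation. The first follow-up film falls at days 28 to 56 (section 7.3), so an earlier failure yields no film.

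**5. How many.** No count is given. AP/lateral films and questionnaires are scheduled together at all five follow-up visits (6 weeks, then 3, 6, 12 and 24 months), and one film at any of them qualifies. A subject loses collected scores only by completing at least one questionnaire and never having a qualifying film.

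**6. Size for a questionnaire mean.** Suppose N implanted subjects have a score at a visit and k of them never had a film. The film-only mean differs from the mean of all N by (k/N) × (mean with film − mean without film). As an assumption, take N = 100 and k = 2, 5 or 10: the shift is 0.02, 0.05 or 0.10 of the difference between the two groups. It is zero if the groups do not differ. The documents give neither k nor the difference.

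**The case against.** The strongest reply is that this is a gap in wording with little practical effect. The plan never says that the questionnaires or the imputation use the section 9.5 population. The synopsis speaks only of the respective population, and section 9.1.6 promises a formal statistical analysis plan in which populations could be assigned. Few subjects would be touched, missing images are tracked as deviations, and early failures stay in the safety population. All of this stands, and it keeps the point small. It does not remove the point: as written, there is one efficacy set and a film is the condition for entering it.

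A reader might infer more, in three ways that the documents do not support:

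- **That the rule inflates the primary lordosis result, or touches every efficacy analysis.** The primary test uses observed data, so a subject without a film is absent under any population definition. Assuming zero gain in such subjects would lower an all-treated mean, but that measures missing data under section 9.3. Rewriting section 9.5 would leave the primary estimate unchanged.
- **That scores of early cage failures are thrown away.** The first post-operative questionnaires are due at the same 6-week visit as the first film. A subject who leaves before then has no scheduled post-operative score to lose; for that subject only the imputation is at issue.
- **That including film-less subjects in the imputation would reveal a much lower mean.** Their lordosis values would be drawn from a model fitted to subjects with films, which does not assign them zero gain. The gain is a robustness check on the right set, and the estimate may move little.

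**Conclusion.** The point holds in limited form. Section 9.5 makes a post-operative film the condition for entering the only efficacy population. On the natural reading, this excludes observed patient-reported scores for an unrelated reason and leaves film-less treated subjects out of the multiple imputation. The observed-data lordosis test, carried-forward lordosis values, radiographic percentages and power are untouched.

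The conclusion rests on two assumptions: that the outcomes under section 9.1 and the imputation of section 9.3 use the section 9.5 set, and that at least a few treated subjects have no film. The number is not given and is probably small. The direction of any shift in the questionnaire results is unknown, although subjects lost through early cage failure are likely to be informative. Severity is low to moderate. The case for acting is that the correction is nearly free.

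**What to change.** Before the data are analysed, in section 9.5 or in the formal statistical analysis plan that section 9.1.6 promises:

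1. Define the efficacy population as all subjects implanted with the study cage.
2. Analyse each endpoint on its own available data, so that a questionnaire analysis needs a questionnaire and not a film. The existing rule on nonmissing denominators already fits this.
3. State in section 9.3 that the multiple imputation covers all implanted subjects.
4. Keep the set with any follow-up film as a sensitivity set for the radiographic endpoints.

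The cost is a few sentences and slightly more analysis work, with no added visit or procedure. The patient-reported results may become slightly less favourable; the observed-data primary result and the radiographic percentages will not change.

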#### **9.6 Safety Patient Population**

All patients who undergo the surgical procedure (lumbar interbody fusion via the transforaminal approach with the AccuLIF Expandable Interbody Fusion Cage with internal supplemental fixation in the form of pedicle screws) will be included in the safety patient population.

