## **7.2 Peri-operative Visit**

During the peri-operative visit, the patient will undergo lumbar interbody fusion via the transforaminal approach with the AccuLIF Expandable Interbody Fusion Cage with supplemental fixation in the form of pedicle screws. Surgical details will be collected including: estimated blood loss (EBL), operative times including skin-to-skin and anesthesia time, implant and screw sizes, and any intraoperative complications will be collected at time of surgery. The length of hospital stay will be recorded upon discharge. Any adverse events occurring during surgery through discharge will be collected and reported.

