## 11.6 Protocol Deviations

Any deviation from this protocol will be reported to Stryker as well as to the EC/IRB according to their reporting procedures. Protocol Deviations for this study include, but are not limited to, the following:

- Informed consent deviations, including but not limited to:

CONFIDENTIAL

This material is the property of Stryker Spine. Do not disclose or use except as authorized in writing by Stryker.  
Page 31

- Study procedures performed prior to informed consent
- Incorrect informed consent version used
- Patient enrolled does not meet the inclusion/exclusion criteria
- Protocol specified study component(s) not implanted
- Visit deviations, including:
  - Unavailable primary endpoint
  - One or more required eCRFs/ images (radiographs/CTs) not done
  - Evaluations occurred outside of protocol specified time window
  - Radiographs / CT not evaluable
  - Missed visit

If the center anticipates a possible protocol deviation, the investigator or SC should contact Stryker for guidance.

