- Post-surgical muscle and tissue pain;
- Injury to other parts of the spine, such as pedicles and transverse processes that may result in temporary or permanent pain or other neurologic symptoms;
- A solid fusion may put more stress on the disc above or below the fusion, which may lead to other complications over time, such as: loss of proper spinal curvature, abnormal motion, disc degeneration, and pain;
- Cessation of growth of the fused portion of the spine;
- Regional Pain Syndrome (sympathetic nerve response) resulting in burning pain, or other abnormal sensation usually usually in the upper extremities. These include, but are not limited to: autonomic dysfunction, reflexive sympathetic dystrophy, or Homer's Syndrome.

It is anticipated that the adverse events associated with the AccuLIF implant will be similar to those of other spinal implants. Specifically, the AccuLIF implant may:

- loosen, break, or move (migrate) with respect to the other

CONFIDENTIAL

This material is the property of Stryker Spine. Do not disclose or use except as authorized in writing by Stryker.  
Page 34

bones of the spine;

- fail to expand within the interbody space (becomes a static cage);
- move or dislodge from the spine (partially or completely), causing injury to nearby organs and tissues in the lower back including blood vessels, nerve roots, spinal cord, dural sac
- fracture the endplate portion of the vertebra, subside, or dislodge a bone fragment during implantation or over time
- Surgical instruments used in the procedure may break, resulting in loose fragments of instrument material, (which is not implantable grade) in the body. Removal of these fragments may cause damage to bones and/or soft tissues. Non-removal of these fragments may cause adverse allergic reactions or injury to sensitive nearby organs.
- Cause adverse / allergic reactions to implant materials (titanium, stainless steel, cobalt-chromium-molybdenum and silicone rubber).
- The bank bone (for the interbody spacer) may transmit infection
- not be positioned properly in the spine, and not maintain proper spinal curvature
- fracture or perforation of the bones of the spine or dislodge bone fragments that may result in temporary or permanent pain or other neurologic symptoms, or surgery;
- cause adverse reactions (titanium)
- collapse at any point post-operatively;
- require another surgery to correct the problem;
- require another surgery to correct improper placement of the device;

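### Read literally, the safety population leaves out subjects in whom the AccuLIF cage was attempted but not implanted, so their recorded complications have no place in the planned safety counts

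*Combined protocol and SAP*

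**What the plan says.** Section 9.6 ties the safety population to a specified operation: "All patients who undergo the surgical procedure (lumbar interbody fusion via the transforaminal approach with the AccuLIF Expandable Interbody Fusion Cage", together with internal fixation by pedicle screws. It does not mention an operation that was started with this plan and finished with another cage or with none.

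The protocol expects that such cases can occur. Section 10.3 states "At the time of study surgery it is required that the following components are implanted" and then lists the cage, the pedicle screws and bone graft. Its table of termination reasons has the row "Study device not implanted Date of surgery", and a separate row for surgery that did not take place. Section 11.6 lists "Protocol specified study component(s) not implanted" among the protocol deviations.

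Collection of events does not depend on implantation. Section 7.2 records intraoperative complications and adds: "Any adverse events occurring during surgery through discharge will be collected and reported". Section 8.1.2 runs reporting from consent to study completion, and 8.4 has events followed until they resolve or stabilise.

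On analysis, 9.2.2 plans descriptive summaries of safety and names no population. The statistical methodology row of the synopsis takes the relevant patient population, restricted to non-missing data, as the denominator for percentages.

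**The concern.** A safety denominator that depends on the device having been implanted is selected on an outcome of the procedure. Section 12.3 expects that the implant may "fracture the endplate portion of the vertebra, subside, or dislodge a bone fragment during implantation or over time", and it also lists instrument breakage, failure to expand and poor positioning. Any of these could lead a surgeon to give up on the cage. If that happens, the subject with the insertion problem is the one whom 9.6 does not name.

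This matters because complications of the AccuLIF cohort, including neurologic ones, are secondary objectives (2.2, 9.1.4). Sections 1.2 and 6.1 also describe the small starting height as meant to protect the endplates and lower the potential for neural injury at insertion. The subjects left out are among those most informative about that description.

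**Working it through.** **Plan's own figure.** The point rests on no figure in the plan. The sample size in 9.4.2 was checked for completeness. A one-sided one-sample t-test with alpha 0.05, a difference of 5 − 3 = 2 degrees and SD 6 reaches 90.2% power at n = 79 and 89.8% at n = 78, so 79 is reproduced. With 20% dropout, 79 / 0.80 = 98.75, or 99, against 100 planned. Changing the safety population does not affect this.

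**Passages side by side.**

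| Question | Section | Answer for a subject with the cage attempted but not implanted |
|---|---|---|
| Is the case foreseen? | 10.3, 11.6 | Yes: a termination reason and a deviation |
| Are events recorded? | 7.2, 8.1.2, 8.4 | Yes, with no implantation condition |
| In the safety population? | 9.6 | Not on the literal wording |
| Added back elsewhere? | 9.2.2, 9.5 | No: 9.2.2 names no population; 9.5 concerns efficacy |
| Denominator for percentages? | Synopsis | The relevant patient population; for safety, 9.6 is the only one defined |

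The events are therefore in the database, but the planned tables do not have to include them.

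The dates also need attention. A termination dated to the day of surgery comes before discharge for anyone who stays in hospital beyond that day. Yet 7.2 collects through discharge, 8.1.2 to study completion, and 8.4 to resolution or stabilisation.

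**Size, by assumption only.** Let N be the attempts, k the abandoned attempts, each with one subject-level event, and e the implanted subjects with an event.

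- As written: e / (N − k)
- Over all attempts: (e + k) / N

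N = 100 takes the planned enrolment as all attempted. The values of k and e are assumptions.

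*No event among implanted subjects (e = 0), k = 3.* As written the rate is 0/97 = 0%, with exact 95% upper limit 1 − 0.025^(1/97) = 3.7%. Over all attempts it is 3/100 = 3%, with Clopper-Pearson limits 0.6% (0.025 quantile of Beta(3, 98)) and 8.5% (0.975 quantile of Beta(4, 97)). With k = 2, the rate over all attempts is 2/100 = 2% (0.2 to 7.0%), against 0/98 as written.

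*Five implanted subjects with an event (e = 5).*

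| k | As written | All attempts |
|---|---|---|
| 1 | 5/99 = 5.1% | 6/100 = 6.0% |
| 2 | 5/98 = 5.1% | 7/100 = 7.0% |
| 5 | 5/95 = 5.3% | 10/100 = 10.0% |
| 10 | 5/90 = 5.6% | 15/100 = 15.0% |

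**Direction.** The understatement depends on abandoned cases having more events than the rest. If 3 cages were abandoned with no event at all and e = 5, the rate as written would be 5/97 = 5.2% against 5/100 = 5.0%, slightly higher.

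**The case against.** The strongest reply is that 9.6 can be read more generously. It says who will be included, without saying that no one else is. Its parenthesis closely follows the description of the planned operation in 7.2, so it may only identify the index surgery. That reading is possible. Two analysts could then produce different denominators from the same data, which is itself a reason to settle the wording.

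Several stronger conclusions are tempting, and the documents do not support them:

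- *The complications go unrecorded.* They do not: 7.2, 8.1.2 and 8.4 require collection and follow-up, and 8.1.1 makes events related to the device or the index procedure reportable.
- *Such subjects must leave the study on the day of surgery.* Section 10.3 introduces its table with "The following is a list of reasons for which subjects may be withdrawn and the date of termination that should be used". The list is permissive, and it gives the date to enter on a form.
- *They are outside the efficacy population too.* Section 9.5 requires only enrolment and some follow-up radiographic assessment. Exclusion would follow only if the subject were withdrawn before any such film.
- *All insertion problems disappear from the rates.* Only subjects left without the cage are affected. An endplate fracture, dural tear or poorly placed cage with the implant left in stays in the safety population.
- *The comparison with published TLIF results is biased.* The sources are still to be named (9.1.6), so nobody can tell whether they count attempts or completed implants.

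It is also fair that safety is descriptive, with no testing (9.2.2), and that the primary endpoint is untouched. This limits the weight of the point but does not remove it.

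**Conclusion.** The point holds in a limited form. On its literal wording 9.6 selects the safety denominator on successful implantation, although 10.3 recognises operated subjects without the device. Their recorded events have no assigned place in the safety summaries. Complication rates could be understated where an insertion problem caused the abandonment.

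The size cannot be derived from the documents. The contrast of 0/97 with 3/100 assumes three abandonments, an event in each, and none among the other 97 subjects, which is the split that shows the effect most sharply. The range of 5.1 to 5.6% as written against 6.0 to 15.0% over all attempts assumes one to ten abandonments, each with an event, and five implanted subjects with an event. If no cage is abandoned, nothing changes. The correction is worth making because it costs little and the omission, where it occurs, can be selective.

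**What to change.** 1. In 9.6, define the safety population as all enrolled subjects in whom the index procedure was begun with intent to implant AccuLIF, whether or not the cage was implanted.
2. In 9.2.2, name that population as the basis for the safety counts and percentages.
3. Report the numbers attempted and implanted, with reasons for non-implantation, so that a reader can also work out rates among implanted subjects.
4. Reconcile the day-of-surgery termination date in 10.3 with adverse event collection and follow-up in 7.2, 8.1.2 and 8.4.

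The cost is mainly wording, and the formal statistical analysis plan anticipated in 9.1.6 could carry the analysis part. Perioperative events are already collected under 7.2, and the sample size does not change. The downside is that the reported complication rate may be slightly less favourable.
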